2.6 Analysis of the key secondary objective

There is no key secondary objective.

2.7 Analysis of secondary efficacy objective

2.7.1 Secondary endpoints

The secondary efficacy objective (i.e., explore the modulation of subcutaneous adipose tissue and skin inflammation from baseline to Week 52) will be assessed using the same two primary efficacy variables, but measured at Week 52.

2.7.2 Statistical method of analysis

For the response of psoriasis skin lesions to the treatment, percentages of patients who have the "event" (as described in Sections 2.5.1 and 2.7.1) at Week 52 will be presented.

This secondary efficacy analysis will be done based on the Full Analysis Set.

2.7.3 Handling of missing values/censoring/discontinuations

See Section 2.5.3.

2.8 Safety analyses

All safety analyses will be based on the Safety Set. Only those scheduled visits which were pre-planned in the protocol will be reported in tables and figures for safety variables.

Treatment groups for evaluation of entire treatment

The summaries of evaluation will be reported for double-blind treatment period and entire treatment period, respectively.

The following groups will be used for double-blind treatment period:

- Secukinumab 300mg
- Placebo

The following groups will be used for entire treatment period:

- Secukinumab 300mg
- Placebo / Secukinumab 300 mg

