## 6.2 Unscheduled visits

Patients may be seen at any time for an unscheduled visit, e.g., if they experience deterioration of psoriasis or suspected AEs. The assessments performed at an unscheduled visit are at the discretion of the investigator/qualified site staff. During an unscheduled visit, study treatment will not be administered.

Novartis	
Amended Protocol Version 02 (Clean)	

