2.4.1.1 Visit windows

Visit-windows will be used for the data that is summarized by visit; they are based on the study evaluation schedule and comprise a set of days around the nominal visit day. For any assessment, there are the protocol defined scheduled visits around which visit windows were created to cover the complete range of days within the study. The visit windows are shown in Table 1-1. In this table, the days are counted since the first dose of study treatment (study days) for safety assessments, and the days are counted since the date of randomization for efficacy assessments. These visit windows apply to measurements taken at every visit. For assessments collected less often different visit windows will be applied as detailed below. When visit windows are used, all visits will be re-aligned, i.e., they will be mapped into one of the visit windows. For example, if the Week 4 visit of a patient is delayed and occurs on Day 46 instead of on Day 29, say, it will be re-aligned to visit window Week 8. In the case of major deviations from the visit schedule, or due to unscheduled visits, several assessments of a patient may fall in a particular visit window (either scheduled or unscheduled). Statistical approaches to handle multiple assessments in a given visit window are specified below.

Of note, patients are allowed to have gaps in visits.

Table 1-1	Assessment	windows	for scho	etieiv haluha
Table 1-1	Assessment	WIIIUUWS	TOT SCITE	eduled visits

Analysis Visit	Week	Scheduled Day	Visit Window	
Baseline	BSL	1	-28 to 1 day	
Week 4	4	29	Day 2-43	
Week 8	8	57	Day 44-71	
Week 12	12	85	Day 72-88	
Week 16	16	113	Day 89-141	
Week 24	24	169	Day 142-197	
Week 32	32	225	Day 198-253	
Week 40	40	281	Day 254-309	
Week 48	48	337	Day 310-351	
Week 52	52	365	Day >=352	

For data which are not collected at every visit (for ex: ______, waist circumference etc.), visit windows will be combined from above Table 1-1. For example, if an assessment is at Week 12 and Week 24 only, Week 12 visit window will extend from Day 2 to Day 88 (combining Week 1 to Week 12 visit windows); Week 24 will extend from Day 89 to Day 197 (combining Week 13 to Week 24). If more than one assessment falls into the interval, the rules defined in following section below are applied.

Assessments from treatment period 2 will not be considered for treatment period 1, and treatment period 1 visits will not be mapped into treatment period 2.

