		day, then select the first one (using the time). If two measurements are taken on the same date/time, then use the first visit number (assuming this is the planned visit).
		If two measurements are taken on the same date/time/CRF visit, then use the average of two assessments
Post-baseline efficacy	All data	The measurement closest to the target day will be used. In the
		event two measurements are
		taken equally apart (e.g., 1 day
		before target date and 1 day
		after), the earlier one will be used.
		If two measurement are taken on the same day then select the first one using eCRF visit number.
Post-baseline safety	Summary visit information	The (non-missing) measurement closest to the

Novartis	For business use only	Page 17
SAP		0

Timing of measurement	Type of data	Rule
	(e.g., laboratory values, vital signs, etc.)	target day will be used. In the event two measurements are taken equally apart (e.g., 1 day before target date and 1 day after), the earlier one will be used.
		If two measurements are taken on the same day then select the first one (using the time).
		If two measurements are taken on the same date/time then use the first eCRF visit number (assuming this is the planned visit). If two measurements are taken on the same date/time/eCRF visit number then take the average value of these two results.
Post-baseline safety and efficacy	Notable abnormalities (e.g., vital signs, PGIC) and CTCAE grading for laboratory values	The most extreme measurement in the window will be used. Note this means a patient can have a notably high and notably low measurement within a window

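### SAP 2.8 restricts safety tables to pre-planned visits, which conflicts with the SAP's own rules for notable-abnormality, maximum-change and most-extreme-shift tables

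*SAP*

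**What the plan says.** SAP 2.8 (Safety analyses) sets a general rule before any individual safety analysis is described: "Only those scheduled visits which were pre-planned in the protocol will be reported in tables and figures for safety variables". It names tables and figures, not listings, and carves out no type of table.

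Other parts of the SAP handle unscheduled data differently:

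- **SAP 2.4.1.1 (Visit windows):** "When visit windows are used, all visits will be re-aligned, i.e., they will be mapped into one of the visit windows". The section expects that one window may hold several assessments of the same patient, unscheduled ones among them. For measurements taken less often, windows are merged. In its example of an assessment made at Weeks 12 and 24, the "Week 12 visit window will extend from Day 2 to Day 88".
- **SAP Table 2-4, row on notable abnormalities and CTCAE grading:** "The most extreme measurement in the window will be used". It adds that a patient may be both notably high and notably low in one window.
- **SAP Table 2-4, tie-break for post-baseline safety values:** when two values share a date and time, the lower visit number is taken, on the assumption that it is the planned visit.
- **SAP 2.1.1.3:** the safety baseline may come from an unscheduled visit.
- **SAP 2.8.3:** maximum increase and decrease from baseline are taken within the treatment period. Shifts to the most extreme laboratory value, if judged appropriate, are taken within a treatment phase.
- **SAP 2.8.4.2:** patients with notable vital signs are counted. All vital signs are listed, and newly occurring notable values have their own listing.

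Protocol 6.2 foresees the data in question: "Patients may be seen at any time for an unscheduled visit". Worsening psoriasis and suspected adverse events are its examples. Protocol Table 6-1 marks haematology, chemistry and vital signs in the unscheduled-visit column.

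**The concern.** Tables of notable abnormalities and extreme values are meant to show whether a patient crossed a threshold at any time in the period. A rule that admits only pre-planned visits works against that purpose. Some unscheduled visits will be prompted by a suspected adverse event, and a laboratory or blood pressure result from such a visit would be left out of these tables.

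The treatment of baseline and follow-up would also be uneven. An unscheduled pre-dose value could set the safety baseline, while an unscheduled post-dose value could not count as an abnormality against it.

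What is at stake is the count of notable values and the reported extremes. Two programmers could each follow a part of the SAP and produce different tables.

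**Working it through.** The plan gives no figure to reproduce. The check compares the rules with one another and counts scheduled assessments.

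**1. Scheduled post-baseline assessments (protocol Table 6-1)**

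| Assessment | Scheduled weeks | Total | In double-blind treatment period |
|---|---|---|---|
| Haematology, chemistry | 12, 24, 52 | 3 | 1 (Week 12) |
| Vital signs | 4, 8, 12, 16, 24, 32, 40, 48, 52 | 9 | 3 (Weeks 4, 8, 12) |

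**2. Planned samples per window.** Merging windows as SAP 2.4.1.1 describes, haematology and chemistry have windows of Day 2–88 (Week 12), Day 89–197 (Week 24) and Day 198 onward (Week 52). Each contains one planned time point. Vital signs likewise have one planned time point in each of their nine windows.

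**3. What the most-extreme rule needs.** With one planned value per window, a rule that picks the most extreme value normally has nothing to choose between. A patient could hardly be notably high and notably low in the same window on the same variable. Apart from planned visits held well off schedule, these provisions have work to do only if unscheduled values are admitted. The tie-break in Table 2-4 likewise presupposes that an unplanned visit can be a candidate.

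**4. Direction of the effect.** Let A be all of a patient's post-baseline values in the period and S the values from scheduled visits, so S is a subset of A. With baseline fixed:

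- max over S ≤ max over A, and min over S ≥ min over A;
- a patient is counted as notable if any value in the set crosses the threshold, so the count under S ≤ the count under A.

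Restricting to S can lower the number of patients with a notable abnormality or leave it unchanged. It cannot raise it.

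**5. Double-blind laboratory tables.** Under the literal rule S normally holds one value, at Week 12. Maximum increase, maximum decrease and most-extreme shift then all rest on that value.

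As a hypothetical case, take an ALT above 3 × ULN at an unscheduled visit on Day 40, back within range at Week 12:

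- By SAP 2.4.1.1 and Table 2-4, Day 40 lies in Day 2–88, and the value is the most extreme in the window. The patient is counted.
- By SAP 2.8 read literally, the Day 40 visit was not pre-planned. The patient is not counted.

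The same data give two results, and the SAP does not say which rule prevails.

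**The case against.** The best defence is that SAP 2.8 controls display, not data. Once visits are re-aligned, an unscheduled value belongs to a planned analysis visit, so the sentence may mean only that planned visit labels appear in the tables. The specific rules in Table 2-4 and SAP 2.8.3 would then govern which values enter, and nothing would be lost. This reading is possible. However, the sentence refers to visits pre-planned in the protocol rather than to analysis visits, and nowhere does the SAP state the milder meaning. The conflict stands, but the loss is a consequence of the literal reading and not a certainty.

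Three stronger inferences are tempting, and the documents do not support them.

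- **That an abnormal value from an unscheduled visit would be absent from all safety output.** Adverse event, serious adverse event and death tables are event-based. Under protocol 7.1 an abnormal laboratory value is an adverse event if it causes signs or symptoms, is clinically significant or needs therapy, so such values are still counted there. Listings fall outside the sentence, and SAP 2.8.4.2 lists all vital signs. The values at risk in the tables are those that cross a numerical threshold without being recorded as adverse events.
- **That the 28 weeks without scheduled laboratory work between Weeks 24 and 52 measure the loss.** That is the length of a gap in the schedule, not a share of values or patients. Planned samples can also fall inside it, because patients who discontinue in the open-label period return for the EOT2 assessments about four weeks after their last dose (protocol 3.1.4).
- **That Table 2-4 already settles all three kinds of table.** Its most-extreme row covers notable abnormalities and CTCAE grading only. Maximum change and most-extreme shift rest on the period wording in SAP 2.8.3, which does not mention unscheduled values.

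**Conclusion.** The point holds as an unresolved conflict between SAP 2.8 on one side and SAP 2.4.1.1, Table 2-4 and 2.8.3 on the other. If SAP 2.8 is applied literally, unscheduled laboratory and vital-sign values leave the notable-abnormality, maximum-change and most-extreme-shift tables, and the counts can only fall or stay the same.

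Exposure is greatest for haematology and chemistry in the double-blind period, with one scheduled post-baseline sample. It is smaller for vital signs, with three in that period and nine overall.

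The size of any understatement cannot be derived. It depends on how often unscheduled visits occur, whether laboratory tests or vital signs are taken at them (protocol 6.2 leaves this to the investigator or site staff), and how often the results cross a threshold without becoming adverse events. The documents give none of these. That abnormal values cluster at unscheduled visits is plausible but not shown.

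The safety summaries are descriptive and the trial is exploratory, so no inferential result depends on this. It still merits correction, because a stated rule contradicts the tables it governs.

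**What to change.** Add a scope statement to SAP 2.8:

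- The restriction to scheduled visits applies only to by-visit descriptive summaries and figures.
- Notable-abnormality tables (including any by CTCAE grade), maximum-change tables and most-extreme-shift tables use all post-baseline values in the relevant treatment period, scheduled or unscheduled.

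The statement should name the maximum-change and shift tables explicitly, since the most-extreme row of Table 2-4 does not cover them. It should also say whether a scheduled visit means the nominal protocol visit or the analysis visit after mapping.

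The cost is one or two sentences in the SAP and matching table specifications. No new data and no change to design or visit schedule are needed.

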#### 3.2 Rationale for study design

The randomized, double-blind, placebo-controlled design used in this study is aligned with the Phase III trials of secukinumab, and with previous studies performed in the indication of chronic plaque psoriasis, and is in accordance with health authority guidelines and feedback, including the United States Food and Drug Administration (FDA).

The study population consists of adult patients with moderate to severe plaque-type psoriasis who are candidates for systemic therapy or phototherapy.

The primary analysis time point of the trial is at Week 12. This is in line with the timing of the primary analysis time point in the secukinumab Phase III trials, and will allow for assessment of efficacy at a point in time for which efficacy data from currently approved biologic therapies are available. Additionally, it is unknown if modulation of adipose tissue by secukinumab will be detectable by the primary time point of 12 weeks. The study design provides for treatment a duration of 52 weeks, which will allow for the assessment of longer-term effects of secukinumab in adipose tissue. For patients randomized to receive placebo at Visit 2/Baseline, the 52-week treatment duration allows these patients the opportunity to receive up to 40 weeks of treatment with secukinumab.

The study population will be described in more detail in Section 4 below.

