## 9.3 Treatments

The number of patients and the length of time (in days) exposed to each treatment will be summarized for the Safety Set.

Concomitant medications will be summarized by treatment using frequency counts and percentages for the Safety Set.

Any condition entered as medical history or current medical condition at baseline will be coded using the MedDRA dictionary for the Safety Set. They will be summarized by system organ class and preferred term of the MedDRA dictionary.

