2.2 Analysis sets

The following analysis sets will be used for the statistical reporting and analyses:

Randomized Set (RAN): The Randomized Set includes all randomized patients.

Safety Set (SAF): The Safety Set includes all patients who received at least one dose of study medication. Patients will be included in the analysis according to treatment received.

Full Analysis Set (FAS): The Full Analysis Set comprises all patients to whom study medication has been assigned. Patients inappropriately randomized (e.g., IRT was called in error for randomization of a screen failed patient) will be excluded from this analysis set. Following the intent-to-treat principle, patients will be analyzed according to the treatment they were assigned to at randomization.

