2.4 Treatments (study treatment, rescue medication, concomitant therapies, compliance)

2.4.1 Study treatment / compliance

The analysis of study treatment and compliance data will be based on the safety set.

The number of secukinumab 1mL syringes, secukinumab placebo injections will be summarized by treatment group by means of contingency tables.

The duration in days will be summarized by treatment, descriptively and using frequencies and percentages for categories "any exposure", "≥1 week", "≥2 weeks", "≥3 weeks", "≥4 weeks", "≥8 weeks", "≥12 weeks", "≥16 weeks", "≥28 weeks", "≥40 weeks" and "≥52 weeks".

Duration of exposure will be defined as the time from first dose of study medication to the last dose plus 84 days or last visit (including follow-up visits) whichever occurs earlier, i.e., for patients who discontinued or have their last visit earlier than 84 days, the end of study

treatment exposure will be the date of the last study visit in the follow-up period or in the corresponding treatment period.

Page 14

Duration of exposure (days) = min (last study visit (including follow-up if applicable) date, last dose date +84) – first dose date +1

Duration of exposure (years) = duration of exposure (days) / 365.25

The analyses of duration of exposure described above will be done for the treatment period up to Week 12 for the interim analysis, with the last category "≥12 weeks".

Compliance of treatment:

Compliance of treatment is defined as percentage of injections administered and will be calculated as the number of injections applied (based on documented study drug administrations and syringe counts as given in the dosage administration record eCRF page) divided by the number of injections scheduled per protocol.

Compliance (%) = 100* (total no of injections administered) / (no. of injections prescribed).

Compliance to study treatment will be summarized descriptively and by categories:

<80%, and 80% - 100%, by treatment groups.

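### SAP 2.4.1 and 2.8 run exposure and adverse events on one clock from the first dose of any study medication, so patients switched from placebo get no planned summary of time or events on secukinumab alone

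*SAP*

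**What the plan says.** SAP 2.8 sets the safety periods: "The summaries of evaluation will be reported for double-blind treatment period and entire treatment period, respectively". For the second of these, "The following groups will be used for entire treatment period": the randomized secukinumab group, and "Placebo / Secukinumab 300 mg" for patients who started on placebo. No third period begins at the switch.

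SAP 2.4.1 defines exposure thus: "Duration of exposure will be defined as the time from first dose of study medication to the last dose plus 84 days or last visit". The formula is "Duration of exposure (days) = min (last study visit (including follow-up if applicable) date, last dose date +84) – first dose date +1". The resulting days are grouped into duration categories, the highest being 52 weeks or more.

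SAP 2.8.1 ties treatment emergence to the first dose of study medication. It counts a patient once per preferred term and closes the window 7 days after the last dose (30 days for serious events).

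Protocol 9.3 requires: "The number of patients and the length of time (in days) exposed to each treatment will be summarized for the Safety Set". Protocol 3.2 says the 52-week design gives placebo patients "these patients the opportunity to receive up to 40 weeks of treatment with secukinumab". On the Safety Set, SAP 2.2 says "Patients will be included in the analysis according to treatment received". SAP section 4 records no departure from the protocol's analyses.

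**The concern.** Patients randomized to placebo receive two treatments in sequence: placebo to Week 12, then secukinumab. A single exposure clock reports the sum of the two under a label naming both, so the duration table overstates how long these patients were on secukinumab and gives days on neither drug. That is the quantity protocol 9.3 asks for.

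The AE table has the same gap. In the entire-period column, an event that began on placebo and one that began on secukinumab look alike. An event that began on placebo and worsened after the switch is not re-flagged, because treatment emergence is judged only against the first dose of study medication. What is lost is a direct summary of secukinumab safety in one third of the randomized patients.

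The structure needed is already in the SAP. Section 2.3 uses a period after Week 12 for disposition and declines to summarize the whole period there. Section 2.4.1.1 keeps the two periods apart when mapping visits. Only the safety and exposure summaries lack the post-switch period.

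**Working it through.** **Inputs.** Protocol Table 6-1: Week 12 dose on Day 85, last dose (Week 48) on Day 337, Week 52 on Day 365, follow-up visit on Day 372. Protocol 9.8: 50 patients on secukinumab, 25 on placebo. SAP 2.4.1: exposure formula with 84 days. SAP 2.8.1: AE window with 7 days. All figures describe completers on schedule, with no dropout.

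**1. The protocol's own figure.** 52 − 12 = 40 weeks; Day 365 − Day 85 = 280 days = 40.0 weeks. This agrees with protocol 3.2.

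**2. The SAP exposure formula for a switched completer.**
- min(372, 337 + 84) − 1 + 1 = 372 days; 372/7 = 53.1 weeks, so the category is 52 weeks or more.
- Placebo days (Day 1 to Day 84): 84. Days from the first secukinumab dose: 372 − 84 = 288; 288/7 = 41.1 weeks, so the category is 40 weeks or more.
- The 288 days exceed the 280 of step 1 by the follow-up week (7) and the inclusive day count (1).
- Without the follow-up visit the total is 365 days (52.1 weeks), which splits into 84 + 281 (40.1 weeks). The misclassification is the same.
- For 25 completers: 25 × 372 = 9,300 patient-days, of which 2,100 are placebo and 7,200 follow the switch.

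**3. The AE window.** Non-serious events count to Day 337 + 7 = Day 344.
- Placebo share for a switched completer: 84/344 = 24.4%.
- Post-switch AE time: 344 − 84 = 260 days; 25 × 260/365.25 = 17.8 patient-years.
- Secukinumab arm: 50 × 344/365.25 = 47.1 patient-years.

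**4. Can the post-switch count be recovered by subtraction?** For one preferred term, let D patients have it in the double-blind period, E in the entire period, S after the switch, and B in both. Counting each patient once gives E = D + S − B, so S = E − D + B with 0 ≤ B ≤ D. The planned tables therefore show only that S lies between E − D and E. With assumed counts D = 5 and E = 8 of 25, S is anywhere from 3 to 8, i.e. 12% to 32%.

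**5. Can exposure be recovered?** Partly. The interim analysis tabulates exposure to Week 12, and means are additive, so the entire-period mean less the Week 12 mean approximates mean secukinumab time. The duration categories do not subtract.

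**The case against.** The strongest reply is that the plan separates more than the two column labels suggest, and much of it stands.

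- A reader might infer that placebo and secukinumab safety cannot be separated at all. The documents do not support that. The double-blind tables show placebo alone, AEs are listed, deaths are summarized by treatment period (SAP 2.8.2), and injections are counted by drug (SAP 2.4.1). Laboratory and vital-sign changes are reported by visit, and protocol 5.1 and 6.7 place assessments before dosing. In switched patients, visits to Week 12 therefore reflect placebo and later visits follow secukinumab. Only summaries taken over the whole period, such as most-extreme laboratory shifts or any-time notable values, can mix the two.
- A reader might extend the protocol 9.3 conflict to AEs. Section 9.3 covers exposure. AEs fall under protocol 9.5.2, which asks for them by treatment group, and the SAP provides that. The Safety Set rule places patients in groups and does not require a patient's time to be split.
- Each treatment in 9.3 could be read as each treatment group. That reading is arguable, but one duration under a label naming two treatments still gives days on neither.
- A reader might expect unequal follow-up to distort the two entire-period columns. At a constant rate, 40% over 53 weeks corresponds to 32.6% over 41 weeks (1 − 0.6^(41/53)). Both columns, however, cover the same calendar length, so an event whose rate does not depend on treatment shows 40% in both.
- The study is exploratory, tests no formal hypothesis, and has a sound randomized comparison in the double-blind table. This limits the weight of the point but does not remove it.

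**Conclusion.** The point holds in two parts. First, the exposure rule places a switched completer in the category of 52 weeks or more with about 41 weeks on secukinumab. It does not deliver the days on each treatment in protocol 9.3, and SAP section 4 does not declare the difference. Second, no planned AE summary or any-time notable-value summary starts at the switch, and the planned AE tables only bound the post-switch count. About 17.8 patient-years of post-switch AE follow-up, against 47.1 in the secukinumab arm, have no AE summary of their own.

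These sizes assume 25 and 50 completers on schedule. The patient-years are upper bounds, since dropout lowers them. The point is worth correcting but does not touch the primary analysis or the placebo-controlled safety comparison.

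**What to change.** 1. In SAP 2.4.1, report placebo days and secukinumab days separately for switched patients, with the secukinumab clock starting at the first secukinumab dose, and apply the duration categories to each.
2. In SAP 2.8, add a post-switch summary of AEs and notable values for placebo-group patients who took secukinumab. Use those patients as the denominator and define treatment emergence from that dose. State which baseline applies to notable changes and assign Week 12 pre-dose values to the placebo period. Leave the double-blind tables as they are.
3. An any-secukinumab column with exposure-adjusted rates is optional; the protocol does not require it. If it is added, its person-time must match the AE window (last dose plus 7 days, or plus 30 for serious events), not the 84-day exposure window. Crude post-switch percentages should not be set beside the full-length secukinumab arm without such an adjustment, because those two periods do differ in length.

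The cost is SAP text, a rule for treatment emergence, baseline and denominator at the switch, and a little extra table programming. The dates are already collected.
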